1.1. Protocol Summary

Trial Title	Revascularisation for Ischaemic Ventricular Dysfunction (REVIVED-BCIS2)					
Aim	To evaluate the efficacy and safety of percutaneous coronary intervention (PCI) compared to optimal medical therapy (OMT) alone for ischaemic left ventricular dysfunction					
Trial Design	Multicentre prospective randomised open controlled trial					
Primary Endpoint	All-cause death or hospitalisation due to heart failure					
Secondary Endpoints	Quality of life score:					
	Kansas City Cardiomyopathy Questionnaire (KCCQ)					
	EuroQol EQ-5D-5L					
	New York Heart Association (NYHA) Functional Class					
	Left ventricular ejection fraction (LVEF) on echocardiography at 6 months and 1 year					
	Hospitalisation for heart failure					
	All-cause death					
	Cardiovascular death					
	Acute myocardial infarction (MI)					
	Appropriate implantable cardioverter defibrillator (ICD) therapy					
	Unplanned further revascularisation					
	Canadian Cardiovascular Society (CCS) angina class					
	Health resource use					
	Brain natriuretic peptide (BNP or NT-proBNP) level					
	Troponin (T or I) level					
	Major bleeding					
Inclusion Criteria	LVEF ≤35%					
	Extensive coronary artery disease (CAD)					
	Viability in at least 4 dysfunctional myocardial segments, that can be revascularised by PCI					
Major Exclusion	Acute MI <4 weeks prior to randomisation (clinical definition)					
Criteria	Acutely decompensated heart failure requiring treatment with inotropes/ventilation/mechanical circulatory support <72 hours prior to randomisation					
	Any contraindication to PCI					

Sample Size and Enrolment	n=700 Start date: 1 st June 2013 Recruitment start date: 1 st September 2013
	Recruitment end date: 30 th April 2020
	Follow-up end date: 30 th April 2022
	Number of centres: 35-40 (listed on trial website)

1.3.4. Clinical Trials Unit (CTU)

The trial is managed by the UKCRC accredited CTU at London School of Hygiene & Tropical Medicine (Registration ID 44).

1.3.8. Recruiting Centres

At each site;

- Heart Failure lead
- PCI lead

(One of which will be designated as the Principal Investigator and the other as a co-investigator)

• Trial Coordinator

A current list of sites is provided on the trial website http://revived.lshtm.ac.uk/

2. Background

2.1. Epidemiology

[figure not shown]
In 2002, it was estimated that approximately 900,000 individuals in the UK had a diagnosis of heart failure and at least 5% of all deaths in the country were related to this condition. At that time, one million in-hospital bed-days per year were estimated to be due to heart failure, with an annual cost to the NHS in excess of £625 million. Furthermore, there is evidence of a rising prevalence of heart failure in the population, with the number of associated hospital admissions expected to increase by around 50% in the next 25 years(1). This emerging epidemic is the likely consequence of a progressively aging population and improved survival from acute coronary syndromes, partly due to more efficient and timely revascularisation techniques. The Framingham Heart Study suggests that the most common cause of chronic heart failure is no longer hypertension or valvular heart disease, as it was in previous decades, but rather coronary artery disease(2). Recent meta-analyses of heart failure trials and large registries have shown that coronary disease is the underlying cause of heart failure in 65% of cases(3, 4), although this may have been an underestimation, given that few of these studies mandated systematic exploration of aetiology.

2.2. Hibernating Myocardium

The concept of viable but dysfunctional myocardium emerged approximately three decades ago, when it was observed that patients undergoing coronary artery bypass surgery for chronic stable angina had improvement or normalisation of left ventricular function following revascularisation(5). The energy utilized during myocyte contraction far exceeds the requirement for sustaining viability and, as such, myocardial tissue may survive in a hypocontractile state in the presence of reduced coronary blood flow or decreased coronary flow reserve, known as hibernation(6). Improvement of blood flow by revascularisation of hibernating myocardium can lead to restoration of regional and global left ventricular function and reversal of adverse remodelling(7-9), provided this is achieved before the onset of irreversible cellular and ultrastructural alterations(10). Potentially reversible, dysfunctional myocardium is characterised by preserved cellular integrity and a degree of contractile reserve, whereas scarring and absence of inducible contraction tend to reflect irreversible myocardial damage. Each of these distinguishing features can be used to predict myocardial viability or the likelihood of functional recovery following revascularisation. The parameter most widely used to determine viability is contractile reserve, which is assessed by measuring the augmentation of function of hypocontractile myocardium, in response to inotropic stimulation. The most commonly used agent is Dobutamine (at doses up to 20 µg/kg/min) while the change in regional and global contractility could be imaged by dobutamine stress echocardiography (DSE) or cine-magnetic resonance imaging (MRI). While MRI allows scar imaging as well as assessment of contractile reserve, at present it is contraindicated in patients with implantable cardioverter defibrillators or pacemakers in situ, which can limit its use in a heart failure population.

Despite variation in the sensitivity and specificity of MRI, DSE, positron emission tomography (PET) and Nuclear Medicine techniques, patients found to have viable myocardium (by any modality) have been shown to have a strong survival advantage following revascularisation compared to medical therapy alone. A meta-analysis of more than 3000 patients in 24 observational studies (in which viability was assessed by single photon emission computed tomography (SPECT), PET or DSE) showed an impressive 80% relative reduction (and 12.8% absolute reduction) in mortality with revascularisation compared to medical therapy in patients found to have significant viable myocardium(8). In contrast, no survival benefit was seen in the absence of viability and even a trend to worse outcome with revascularisation.

These data also argue against a strategy of revascularising all patients with heart failure and coronary disease, regardless of viability; mortality following coronary artery bypass graft (CABG) surgery in patients without viability was more than double that observed in those who did have viable myocardium.

A more recent analysis of 14 non-randomised studies suggests that the findings of the Allman meta-analysis have not changed despite changes in revascularisation techniques and medical therapy(11). It has traditionally been held that completeness of revascularisation (in relation to the angiographic findings) is a major determinant of outcome in ischaemic cardiomyopathy(12); whether regional viability can be used to guide the extent (and hence the mode) of revascularisation in a given patient, remains untested to date.

Notwithstanding the compelling nature of these small studies, there is a lack of consensus on the role of revascularisation in patients with heart failure owing to the absence of adequately powered randomised controlled trials (RCTs) in this field(13-15). Furthermore, there have been major advances in medical therapy for heart failure during the last decade and the incremental benefit of revascularisation in contemporary practice is unknown. REVIVED-BCIS2 will be the largest contemporary randomised comparison of percutaneous revascularisation (with optimal medical therapy (OMT)) versus OMT alone in patients with heart failure and viable myocardium, and is expected to definitively resolve the role of this treatment.

2.3. CABG surgery for ischaemic cardiomyopathy

CABG surgery is considered an appropriate treatment for impaired left ventricle (LV) function in the presence of significant proximal coronary disease, regardless of whether the patient has angina(13-16). These recommendations were based on data from registries and cohort studies that were carried out more than 20 years ago, before the routine use of medical therapies that have been shown to improve survival and symptoms in this group of patients. The Coronary Artery Surgery Study (CASS) registry included 651 (of a total of approximately 20,000) patients who had a left ventricular ejection fraction (LVEF) <50%, 231 of whom received CABG surgery. CABG provided a mortality benefit over medical therapy only in the subgroup of patients with severe LV dysfunction (ejection fraction (EF) <25%), where angina was the predominant symptom, rather than heart failure(17). The Duke registry of 1391 patients with ischaemic cardiomyopathy (EF <40%), treated over a period of 25 years, demonstrated a sustained survival benefit in the group receiving CABG surgery (339 patients) compared to those treated with medical therapy alone(18).

The landmark Surgical Treatment for Ischemic Heart Failure (STICH) trial is the only completed RCT to date that addressed this question(19). This was an international multicentre, openlabelled RCT that enrolled 1212 patients with LV dysfunction (EF <35%) with follow up for an average of 4.7 years. The main hypothesis was that a strategy of coronary artery bypass grafting and OMT compared with OMT alone would reduce the primary outcome of all-cause mortality. The primary outcome was not found to be significantly different between groups (41% OMT versus 36% CABG, p=0.12). There was a trend for a reduction in the secondary outcome of cardiovascular mortality in the CABG treated group, which did not quite make statistical significance (p=0.05). The Surgical Treatment for Ischaemic Heart Failure Extension Study (STICHES) reported longer-term mortality data from the STICH trial; 98% of the study cohort was followed up for a median of 9.8 years, during which time 59% of patients assigned to CABG died versus 66% in the medical therapy group (hazard ratio 0.84; 95% confidence interval, 0.73-0.97; p=0.02)(20). Death from cardiovascular causes and several pre-specified composite secondary endpoints also occurred less often in the CABG group. Patients with more severe coronary artery disease, a left ventricular aneurysm suitable for surgical reconstruction, who were classified as being Hispanic/Latino/non-white or were younger than 60 years had the greatest survival benefit with revascularisation (p values for interaction 0.04, 0.03, 0.02 and 0.18 respectively)[60].

Several considerations should be taken into account when interpreting the above data. Firstly, although the trial at its onset mandated the presence of viability for enrolment, due to slow recruitment this was removed from the protocol; as a result, a patient population with both non-viable and viable myocardium were enrolled. Secondly, on average 2 patients were enrolled per centre per year, reflecting the fact that this was a difficult trial to recruit to, and may indicate selection bias. Importantly, the CABG procedure itself conferred a higher 30-day mortality than with medical therapy, which may have ameliorated any benefit seen with revascularisation, an effect which lasted for more than 2 years. This finding is in keeping with registry data on CABG surgery: perioperative mortality rates in patients with LV dysfunction have been shown to be between 5% and 30%; and the risk increasing with age, comorbidities and degree of LV impairment(21). The relative risk of early death following CABG surgery in patients with severe LV dysfunction is 3- to 4-fold higher than in those with mild dysfunction or preserved systolic function(22-24). However for patients who survive this early mortality hazard, there may be a long-term mortality benefit from CABG. Another consideration is the age of the population enrolled in STICH(ES) and whether this relatively young population are representative of the average heart failure patient. In STICHES, the reduction in mortality was about 25% for those aged <60 years (slightly more than half of all patients) but only 9% in those aged >60 years.

Furthermore, patients with left main coronary stenoses (who represent the extreme end of the spectrum of coronary disease and therefore are at highest risk of cardiovascular events) were excluded from the trial. Finally, the STICH investigators did not systematically exclude patients with non-ischaemic cardiomyopathy with co-existent coronary disease; a minimum coronary disease severity was not mandated and, as a consequence, 40% of the entire cohort had single or 2 vessel disease only. Potential inclusion of non-ischaemic cardiomyopathy patients would be expected to dilute any beneficial effects of revascularisation.

2.4. PCI for ischaemic cardiomyopathy

Numerous comparisons have been made between percutaneous coronary intervention (PCI) and CABG surgery for patients with symptomatic coronary disease or evidence of significant reversible ischaemia, but most of the large RCTs excluded patients with impaired left ventricular function (EF <30%)(26-28). Less than 2% of all patients included in the largest and most recent RCT, the Synergy between PCI with Taxus and Cardiac Surgery (SYNTAX) trial, had significant LV impairment (EF <30%) at baseline(29). A meta-analysis of 10 such trials has

found similar 5-year survival following surgery or PCI in the combined cohort, as well as in the subgroup (17% of all patients) who had modest LV dysfunction(30). We recently reported mortality rates of 1.3% and 6% at one and 6 months respectively, following PCI in 301 patients with severely impaired LV function (EF 24%) and severe coronary disease (British Cardiovascular Interventional Society (BCIS-1) Jeopardy Score (JS) of 10/12)(31). Long-term all-cause mortality assessment in this cohort was completed in October 2011, by tracking the database of the Office for National Statistics in the UK. These data provide the best contemporary indication of the utility of PCI in ischaemic cardiomyopathy. All-cause mortality at a median of 51 months (range 28-70) was 33%(32). Notwithstanding the inherent difficulties of carrying out a non-randomised comparison, it is worth noting that mortality in the 600 medically treated patients in STICH was 46% at a median of 56 months (range 12-72), despite having better overall LV function (EF 28%) and a lower coronary disease burden than the contemporaneous BCIS-1 cohort. These results may suggest that PCI may be the preferred mode of revascularisation for patients with ischaemic cardiomyopathy who have suitable coronary anatomy. The ability to carry out surgical ventricular reconstruction has also been traditionally considered an indication for CABG surgery rather than PCI, but Hypothesis 2 of the STICH trial suggests that ventricular restoration does not offer survival or functional benefit over revascularisation alone(33).

There have been a few non-randomised comparisons of the two modalities in patients with poor LV function. In the pre-stent era, observational studies suggested better early outcomes but less complete revascularisation and more mid-term repeat revascularisation procedures following balloon angioplasty than surgery, with similar long-term survival following either treatment(12, 34). The Angina With Extremely Serious Operative Mortality Evaluation (AWESOME) investigators combined the data from randomised and registry cohorts in a prespecified subgroup analysis and demonstrated equivalent 3-year survival following surgery or bare-metal stent PCI(35). The advent of drug-eluting stents has vastly reduced the incidence of restenosis and has facilitated a greater degree of revascularisation with PCI, which are particularly pertinent factors in the treatment of ischaemic cardiomyopathy(36). A recent observational study has confirmed these theoretical benefits by demonstrating comparable mortality at 15 months following drug-eluting stent PCI or CABG surgery, although there was a greater improvement in New York Heart Association (NYHA) functional class with surgery, possibly due to more complete revascularisation(37). However, these studies were relatively underpowered retrospective analyses that included patients who had significant angina and were not balanced in terms of baseline characteristics or completeness of revascularisation. At present, although conceptually appealing, there is no randomised evidence supporting the use of PCI for patients with ischaemic cardiomyopathy and predominant symptoms of heart failure, rather than angina. There is clearly a need for systematic evaluation of the safety and efficacy of this treatment by a RCT. Furthermore, there have been major advances in medical therapy for heart failure during the last decade and the incremental benefit of revascularisation in contemporary practice is unknown. REVIVED-BCIS2 will be the largest contemporary randomised comparison of percutaneous revascularisation (with OMT) versus OMT alone in patients with heart failure and viable myocardium, and is expected to definitively resolve the role of this treatment.

3. Hypothesis

Compared to OMT alone, PCI improves event-free survival in patients with ischaemic cardiomyopathy and viable myocardium.

4. Endpoints

An independent clinical events committee (CEC), who are blinded to treatment assignment, will centrally adjudicate and validate selected endpoints where validation is necessary.

4.1. Primary Endpoint

All-cause death or hospitalisation due to heart failure. This composite endpoint will be collected over the entire duration of follow-up in the trial.

4.2. Major Secondary Endpoints

LVEF on echocardiography at 6 months and 1 year

Quality of life score:

- Kansas City Cardiomyopathy Questionnaire (KCCQ)
- EuroQol EQ-5D-5L

NYHA Functional Class

4.3. Other Secondary Endpoints

Cardiovascular death
All-cause death
Hospitalisation due to heart failure
Acute myocardial infarction (MI)
Appropriate implantable cardioverter defibrillator (ICD) therapy
Unplanned further revascularisation
Canadian Cardiovascular Society (CCS) angina class
Health resource use
Serial Troponin (T or I) levels
Serial brain natriuretic peptide (BNP or NT-proBNP) levels
Major bleeding

4.4. Endpoint Definitions

Acute Myocardial Infarction

1. Spontaneous MI (>48 hrs after PCI/CABG)

Detection of a rise and/or fall of cardiac biomarkers (preferably Troponin (T or I), with at least one value higher than the 99th percentile upper reference limit (URL)*) AND symptoms consistent with ischaemia OR dynamic electrocardiogram (ECG) changes (including >1mm ST elevation, new Left Bundle Branch Block (LBBB) >1mm ST depression, >3mm T wave inversion).

2. Peri-procedural MI (<48 hrs after PCI/CABG)*

Following PCI: Troponin (T or I) >5 times the 99th percentile URL (or 5 times the baseline value if this is higher than the URL) in combination with any of the following: (i) evidence of prolonged ischaemia (>20 min) as demonstrated by prolonged chest pain and/or ischaemic ST changes; (ii) new pathological Q waves; (c) angiographic evidence of a flow limiting complication, such as of loss of patency of a side branch, persistent slow-flow or no-reflow, embolisation; or (d) imaging evidence of new loss of viable myocardium or new regional wall motion abnormality.

Following CABG: Troponin (T or I) >10 times the 99th percentile URL (or 10 times the baseline value if this is higher than the URL) in combination with any of the following: (i) new pathological Q waves; (ii) angiographically documented new graft or new native coronary artery occlusion; or (iii) imaging evidence of new loss of viable myocardium or new regional wall motion abnormality.

3. Sudden death

Cardiac arrest accompanied by new ST elevation/LBBB on ECG and/or evidence of fresh coronary thrombus at autopsy/angiography.

* In addition to classifying patients dichotomously, on the basis of the 2012 Universal Definition of MI(38), as having suffered a periprocedural MI or not, baseline and peak Troponin (T or I) levels measured within 24 hours of a procedure will be recorded. This will provide a continuous outcome measure of periprocedural myocardial injury and will also allow subsequent reclassification in the event of further revisions to the Universal Definition during the course of the trial.

Hospitalisation for heart failure (39, 40)	Hospital admission (lasting >24 hours) for deteriorating symptoms or signs of heart failure, where there is a documented diagnosis of heart failure and the patient receives initiation or intensification of treatment for heart failure. Initiation or intensification of treatment includes at least one of the following: increase in oral diuretic dose or addition of another oral diuretic; intravenous diuretic therapy; intravenous vasoactive therapy (vasodilator, inotrope or vasopressor); mechanical circulatory support (MCS) (including intra-aortic balloon pump (IABP), Impella, extra-corporeal membrane oxygenation (ECMO)); or cardiac transplantation.
	Heart failure during or after the assigned PCI procedure itself is defined as prolongation of the planned admission by at least 24 hours due to acute heart failure requiring initiation or intensification of treatment as defined above. Prolongation of hospital admission in patients who have prophylactic pre-PCI insertion of a mechanical support device (IABP, Impella or ECMO) should not be recorded as having a heart failure hospitalisation UNLESS there are features of heart failure requiring initiation or intensification of treatment as defined above.
	Elective admission for implantation or revision of ICD/cardiac resynchronisation therapy (CRT) devices will NOT constitute an endpoint.
Unplanned revascularisation	PCI group: Any unplanned target vessel or non-target vessel revascularisation by PCI or CABG following index PCI, excluding provisional staged PCI (with plan documented at the index procedure). OMT group: Any revascularisation by PCI or CABG.
Appropriate ICD therapy	At least one ICD shock or episode of anti-tachycardia pacing for documented ventricular tachycardia (VT) or ventricular fibrillation (VF).
Cardiovascular death	All deaths where there is no clinical or post-mortem evidence of a non-cardiovascular aetiology.

Major Bleeding

Major bleeding will be defined using the Bleeding Academic Research Consortium (BARC) categories below:

Type 3

Type 3a

- Overt bleeding plus haemoglobin drop of ≥30 to <50g/L (provided haemoglobin drop is related to bleed)
- Any transfusion with overt bleeding

Type 3b

- Overt bleeding plus haemoglobin drop ≥50g/L (provided haemoglobin drop is related to bleed)
- Cardiac tamponade
- Bleeding requiring surgical intervention for control (excluding dental/nasal/skin/haemorrhoid)
- Bleeding requiring intravenous vasoactive drugs

Type 3c

- Intracranial haemorrhage (does not include microbleeds or haemorrhagic transformation; does include intraspinal)
- Subcategories; confirmed by autopsy, imaging or lumbar puncture (LP)
- Intra-ocular bleed compromising vision

Type 4: CABG-related bleeding

- Perioperative intracranial bleeding within 48 hours
- Reoperation following closure of sternotomy for the purpose of controlling bleeding
- Transfusion of ≥5 units of whole blood or packed red blood cells within a 48-hour period
- Chest tube output ≥2L within a 24-hour period
- If a CABG-related bleed is not adjudicated as at least a Type 3 severity event, it will be classified as 'Not a bleeding event'

Type 5: fatal bleeding

Type 5a

 Probable fatal bleeding: no autopsy or imaging confirmation, but clinically suspicious

Type 5b

Definite fatal bleeding: overt bleeding or autopsy or imaging confirmation

5. Safety Reporting

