8.2. Crossover

In patients randomly assigned to receive OMT, revascularisation by PCI or CABG during the trial should only be considered in one of the following circumstances:

- Readmission with an acute coronary syndrome (ACS), including ST-elevation myocardial infarction (STEMI) and non-STE events. The diagnosis of ACS will be based on the presence of typical ischaemic symptoms as well as a rise in cardiac biomarker levels or dynamic ST deviation on ECG.
- Deterioration in exertional angina to ≥CCS class 3 level symptoms.
- Resistant ventricular arrhythmias considered to be ischaemic in aetiology.

This trial will be a comparison of strategy, rather than technique, and the projected event rates and hazard ratio allow that OMT patients may undergo subsequent revascularisation. As such, no additional adjustments have been made to the power calculation to account for unplanned revascularisation in the OMT arm.

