4.3 Randomisation and Blinding

Randomisation of the treatment assignment will be stratified by centre using randomly permuted blocks of varying size, with 1:1 allocation between the PCI and OMT alone arms. This will be done on a secure web-based service through the Clinical Trials Unit at LSHTM. It is recommended that index PCI be carried out as close as possible to randomisation to minimise the incidence of major adverse cardiovascular events prior to the assigned treatment.

Due to the nature of the intervention being assessed (PCI versus medical therapy) this is an open trial and patients / investigators will not be blinded to treatment assignment. However, independent personnel who are blinded to treatment assignment will centrally adjudicate all major endpoints.

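### Heart failure arising in hospital around a revascularisation is a primary event only after the assigned PCI, so one half of the primary composite is captured differently by arm

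*Protocol*

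**What the plan says.** Protocol section 4.1 makes hospitalisation for heart failure one half of the primary endpoint, collected over all follow-up. Section 4.4 gives two routes to it.

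- **General route:** "Hospital admission (lasting >24 hours) for deteriorating symptoms or signs of heart failure", with a documented diagnosis and treatment started or stepped up.
- **Peri-procedural route:** "Heart failure during or after the assigned PCI procedure itself is defined as prolongation of the planned admission by at least 24 hours", with the same treatment requirement.

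A further sentence, on prophylactic mechanical support, begins "Prolongation of hospital admission in patients who have prophylactic pre-PCI insertion of a mechanical support device (IABP, Impella or ECMO) should not be recorded". It speaks of PCI without the qualifier *assigned*.

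Section 8.2 says that for OMT patients "revascularisation by PCI or CABG during the trial should only be considered in one of the following circumstances", and lists acute coronary syndrome, worsening exertional angina and resistant ventricular arrhythmia. The same section describes the trial as comparing strategies rather than techniques.

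On adjudication, the opening of protocol section 4 refers to a committee "who are blinded to treatment assignment, will centrally adjudicate and validate selected endpoints where validation is necessary". SAP section 4.3 says that "independent personnel who are blinded to treatment assignment will centrally adjudicate all major endpoints".

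**The concern.** The peri-procedural route extends the endpoint to heart failure that prolongs a stay begun for another reason. It is tied to the assigned PCI and to a planned admission. Nearly every PCI-arm patient is exposed to it by design, and no OMT patient is.

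In a comparison of strategies analysed by intention to treat, revascularisation of an OMT patient is part of the OMT strategy, and its complications belong to that arm. If acute heart failure around a crossover procedure is not captured while the same event around the assigned PCI is, the primary hazard ratio and the heart failure hospitalisation comparison both lean against PCI.

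There is also a practical difficulty. Whether a PCI was the assigned one is a question about allocation, yet the people applying the definition are stated not to know the allocation.

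**Working it through.** **1. Which events each rule reaches**

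| Acute heart failure arising in hospital… | General route | Peri-procedural route |
|---|---|---|
| around the assigned PCI (PCI arm) | no, if admitted only for the PCI | yes |
| around crossover PCI or CABG (OMT arm) | only if heart failure was a reason for admission | no |
| around an unplanned repeat procedure (PCI arm) | only if heart failure was a reason for admission | no |

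By contrast, the peri-procedural MI definition in the same section applies to PCI and CABG whatever the assignment.

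**2. The plan's own figures**

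Inputs from protocol section 8.1: 300 events, HR 0.7, 5% significance (two-sided assumed), 36% OMT event rate at two years.

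- Power = Φ(|ln 0.7| × √300 / 2 − 1.96) = Φ(3.09 − 1.96) = 87.1%, against a stated figure of over 85%.
- PCI two-year rate = 1 − 0.64^0.7 = 26.8%, stated as 27%.

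Both reproduce.

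**3. How many OMT events could be missed**

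The documents give neither a crossover rate nor a rate of heart failure around crossover procedures. Both are assumptions here: crossover 5–20%, heart failure in 3–10% of those.

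Missed first events = 350 × crossover × heart failure rate:

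- low: 350 × 0.05 × 0.03 = 0.5
- middle: 350 × 0.10 × 0.05 = 1.75
- high: 350 × 0.20 × 0.10 = 7.0

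**4. Split of events by arm**

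- OMT hazard = −ln(0.64)/2 = 0.223 per year; PCI hazard = 0.7 times that.
- From the dates in SAP Appendix 2, recruitment lasted 6.55 years (taken as rising linearly), with 2.03 years of further follow-up. Losses are set at 5%.
- Integrating the exponential event probability over entry times gives about 201 OMT and 160 PCI events, 361 in all.
- Scaled to the protocol's 300 events: 300 × 201/361 = 167 OMT and 133 PCI.

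**5. Effect on the hazard ratio and power**

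Apparent HR = 0.70 × E / (E − m), where E is the number of OMT events and m the number missed. Power uses the formula in step 2 with m fewer events.

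| Missed m | HR, 300 events | Power | HR, 361 events | Power |
|---|---|---|---|---|
| 0 | 0.700 | 87.1% | 0.700 | 92.3% |
| 0.5 | 0.702 | 86.4% | 0.702 | 91.9% |
| 1.75 | 0.707 | 84.8% | 0.706 | 90.9% |
| 7.0 | 0.731 | 76.6% | 0.725 | 85.6% |

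This holds OMT person-time fixed, which is what results if missed patients go on to have later counted events at the arm's average rate. A harsher accounting keeps every missed patient event-free to the end. With 300 events split as cumulative incidences of 48.5% (OMT) and 37.2% (PCI), removing 7 OMT events leaves 46.5%, and ln(1 − 0.372)/ln(1 − 0.465) gives an HR of about 0.74. Patients who have just had acute heart failure are unlikely to be free of later events, so 0.73 is the more realistic extreme. Neither figure takes credit for missed events around unplanned repeat procedures in the PCI arm, which would offset part of the shift.

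**The case against.** Several points on the other side are sound.

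- **Silence is not exclusion.** A reader might infer that the protocol bars crossover heart failure events from the endpoint. It does not. It provides no route for them, which leaves the outcome to whoever applies the text. Heart failure that was a reason for admission counts in either arm, and so does every death.
- **The contrast is not purely arm against arm.** A reader might infer that all harm of revascularisation is charged to PCI and none to OMT. Unplanned repeat procedures in the PCI arm fall in the same gap, as does heart failure arising during any other non-cardiac-failure admission in both arms. What remains is that the extra route exists for one arm only.
- **Blinding is strained, not shown to fail.** A reader might infer that blinded adjudication cannot hold. The protocol limits adjudication to selected endpoints, the adjudication procedure is not shown, and the label could be attached outside the committee. A planned PCI soon after randomisation hints at the arm however the rule is worded. The two complaints also pull against each other: a truly blinded committee might count an elective crossover event because it could not tell that the PCI was unassigned.
- **The planned-stay wording has a purpose.** A planned admission has an expected length that can be exceeded; an emergency admission does not. Simply deleting the restriction would leave prolongation with nothing to be measured against. This stands, and the fix has to deal with it.

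**Conclusion.** As written, the heart failure component of the primary composite has a route to an event that only the PCI arm can use, although the protocol itself expects revascularisation in the OMT arm. The likely result is a small bias against PCI: about 0.5 to 7 OMT first events, with a true hazard ratio of 0.70 appearing as 0.70 to about 0.73. In the extreme case power would be about 77% on 300 events, or about 86% on the 361 that the stated rate and dates imply. The middle case moves the hazard ratio to about 0.71.

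All of these sizes rest on assumed crossover and heart failure rates. The difference in capture follows from the wording alone, as does the rule's dependence on assignment. The documents do not support a claim that the primary comparison is seriously distorted or that adjudication is unblinded. This is a cheap improvement to an endpoint definition.

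**What to change.** Make the rule in section 4.4 independent of assignment, as the MI definition already is. For example:

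> Heart failure during or after any coronary revascularisation (PCI or CABG; assigned, staged or unplanned; either arm) is an event if treatment is initiated or intensified as defined above and the hospital stay is prolonged by at least 24 hours. For a planned admission, prolongation is judged against the planned stay. For an unplanned admission, it means at least 24 further hours in hospital that the blinded committee attributes to acute heart failure.

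Word the prophylactic-support sentence to the same scope and carry the text into the adjudication procedure. If an assigned/unassigned label is wanted for description, the trials unit can derive it from procedure dates after adjudication.

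The cost is a change to one paragraph and a few more admissions to adjudicate. Those are already identifiable, because any revascularisation in the OMT arm and any unplanned one in the PCI arm is recorded as a secondary endpoint. The real downside is some added judgement for unplanned stays, where time attributable to heart failure must be separated from time attributable to the acute event or the surgery.
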